^u FSH will be measured for any suspected postmenopausal female subjects with at least 12 months of continuous spontaneous amenorrhea.

^v A single blood sample will be collected for the G6PD activity test.

█ [Redacted]

^x On Days 3, 5, and 11, the following parameters will be measured: lactate dehydrogenase, total and direct bilirubin, alkaline phosphatase, aspartate aminotransferase, alanine aminotransferase, and gamma glutamyl transferase.

^y Blood samples will be collected for PK analysis of VX-152, VX-661, M1-661, IVA, and M1-IVA. On Day 1, samples will be collected before dosing (0 hours) and at 1, 2, 4, and 6 hours after dosing (relative to morning dose). On Day 8, a predose sample will be collected before the morning dose of study drug (0 hours). On Day 15, samples will be collected before dosing (0 hours) and at 1, 2, 4, 6, and 8 hours after dosing. At ETT Visits, a single blood sample for PK analysis will only be collected from subjects who discontinued study drug after Day 1, but before Day 15 PK was collected.

^z The last dose of VX-661/IVA will be the morning dose on Day 29.

Table 3-2 Study VX16-152-102: Schedule of Assessments for Part 2, Cohort 2A

Event/Assessment ^a	Screening	Run-in Period		Treatment Period ^b					Washout Period	ETT Visit ^c	Safety Follow-up 28 (± 7) Days After Last Dose ^d
	Days -56 to -29 ^e	Day -28 (± 1 day)	Day -14 ^f (± 1 day)	Day 1	Days 3 and 5 ^g (or Days 4/6 or Days 3/6) ^h	Day 8 (± 1 day)	Day 11 ^g (± 1 day)	Day 15 (± 1 day)	Day 29 (± 3 days)		
VX-152 or placebo dosing ^{aa}				Day 1 through Day 15							
AEs, medications ^{bb} , treatments and procedures	Continuous from signing of the ICF through the Safety Follow-up Visit										

^{aa} The last dose of VX-152 or placebo will be the morning dose on Day 15.

^{bb} Refer to [Section 9.4](#) for details.

Table 3-3 Study VX16-152-102: Schedule of Assessments for Part 2, Cohort 2B

Event/Assessment ^a	Screening	Run-in Period		Treatment Period ^b					Washout Period	ETT Visit ^c	Safety Follow-up 28 (± 7) Days After Last Dose ^d
	Days -56 to -29 ^e	Day -28 (± 1 day)	Day -14 ^f (± 1 day)	Day 1	Days 3 and 5 ^g (or Days 4/6 or Days 3/6) ^h	Day 8 (± 1 day)	Day 11 ^g (± 1 day)	Day 15 and Day 29 (± 1 day)	Day 43 (± 3 days)		
Informed consent	X										
Randomization ⁱ				X							
Demographics	X										
Medical history	X										
Ophthalmological history	X										
CFQ-R ^{j,k}				X		X		X	X	X ^l	X

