8.1.4 Washout Period (Part 2)

The Washout Period will last approximately 2 weeks and is designed to allow for the measurement of off-treatment effects. Subjects will continue to receive VX-661/IVA during the Washout Period.

Study visits during the Washout Period will occur as shown in [Table 3-2](#) and [Table 3-3](#). All visits should occur within the windows specified.

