10 STUDY DRUG ADMINISTRATION AND MANAGEMENT

Study drug refers to VX-152, VX-661/IVA, IVA, and their matching placebos.

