For Part 2, the TE period will be defined separately for the Run-In Period, and the Treatment Period:

- The TE period for the Run-in Period will include the time from the first dose of study drug in the Run-in Period to: (1) the last day prior to the first dose of study drug in the Treatment Period for subjects who complete the Run-in Period and continue to the Treatment Period, or (2) the SFU Visit for subjects who did not continue to the Treatment Period and have an SFU Visit, or (3) 28 days after the last dose of study drug in the Run-in Period for subjects who do not have an SFU Visit (e.g., subjects who do not meet the criteria to enter the Treatment Period and re-enter Study 661-110). Only data collected up to the end of study for a subject will be included in analysis.
- The TE period for the Treatment Period will include the first dose of study drug in the Treatment Period to: (1) the SFU Visit, or (2) 28 days after the last dose of study drug for subjects who do not have an SFU Visit (e.g. subjects whose Early Treatment Termination (ETT) Visit occurs 3 weeks or later following the last dose of study drug and the ETT visit replaces the SFU visit, or who leave the study early and re-enter Study 661-110). Only data collected up to the end of study for a subject will be included in analysis.

Unscheduled visits: Unscheduled visit measurements will be included in analysis as follows:

- In scheduled visit windows per specified visit windowing rules.
- In the derivation of baseline/last on-treatment measurements.
- In the derivation of maximum/minimum on-treatment values and maximum/minimum change from baseline values for safety analyses.
- In individual subject data listings as appropriate.

Visit windowing rules: The analysis visit windows for protocol-defined visits are provided in Appendix B.

Spirometry ($ppFEV_1$) will be used for both efficacy and safety purposes. For efficacy analysis, the assessments will follow the visit windowing rules for efficacy. For safety analysis, the assessments at 5 hours post-dose on nominal days 1 and 15 will be used.

Incomplete/missing data will not be imputed, unless specified otherwise.

Outliers: No formal statistical analyses will be performed to detect or remedy the presence of statistical outliers, unless specified otherwise.

Multiplicity: There will be no multiplicity adjustment for performing multiple hypothesis tests, unless specified otherwise.

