8.5 Safety Analysis

The overall safety profile of study drug will be assessed in terms of the following safety and tolerability endpoints:

- Adverse events
- Clinical laboratory values (hematology, chemistry, coagulation, and urinalysis)
- Standard 12-lead electrocardiograms
- Vital signs
- Pulse oximetry

Safety endpoints will be analyzed based on the Safety Set. Only a descriptive analysis of safety will be performed. Safety results for treatment groups in Part 2 Cohort 2A and Part 2 Cohort 2B will be presented separately, and overall.

For Part 2, the Safety Set refers to the Safety Set for the Treatment Period.

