8.5.1 Adverse Events

AEs will be classified as pretreatment AEs, TEAEs, or post-treatment AEs, defined as follows:

For Part 1:

Pretreatment AE: any AE that started before the first dose date of study drug

TEAE: any AE that worsened (either in severity or seriousness) or that was newly developed at or after the first dose date of study drug through the end of the TE period

Post-treatment AE: any AE that worsened (either in severity or seriousness) or that was newly developed beyond the TE period

For Part 2:

Pretreatment AE: any AE that started before the first dose date of study drug

TEAE during the Run-in Period: any AE that worsened (either in severity or seriousness) or that was newly developed at or after the first dose date of study drug through the end of the TE period for the Run-in Period

TEAE during the Treatment Period: any AE that worsened (either in severity or seriousness) or that was newly developed at or after the first dose date of study drug through the end of the TE period for the Treatment Period

Post-treatment AE: any AE that worsened (either in severity or seriousness) or that was newly developed beyond the TE period

For AEs with completely missing or partially missing start dates, if there is no clear evidence that the AEs started before or after study treatment, the AEs will be classified as TEAEs.

Details for imputing missing or partial start dates of adverse events are described in Appendix G.

An adverse event overview table will be provided for the TE period (TE period for the Treatment Period for Part 2) by treatment group, for the following:

- Number of TEAEs (total number of TEAEs only)
- Subjects with any TEAEs
- Subjects with TEAEs by Strongest Relationship
- Subjects with TEAEs by Maximum Severity
- Subjects with TEAEs Leading to Treatment Discontinuation
- Subjects with TEAEs Leading to Drug Interruption
- Subjects with Serious TEAEs
- Subjects with TEAE Leading to Death

Summaries will be presented by MedDRA system organ class (SOC) and preferred term (PT) using frequency counts and percentages (i.e., number and percentage of subjects with an event). When summarizing the number and percentages of subjects, subjects with multiple occurrences of the same adverse event or a continuing adverse event will be counted once, and only the maximum severity level will be presented in the severity summaries, and the strongest relationship level in the relationship summaries.

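### In Part 2 the treatment-emergent window runs nominally 42 days past the last VX-152 dose, and no planned AE table isolates time on VX-152, so an on-drug AE excess is diluted

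*SAP*

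**What the plan says.** SAP 8.1 sets the Part 2 treatment-emergent (TE) period for the Treatment Period so that it "will include the first dose of study drug in the Treatment Period to: (1) the SFU Visit". For subjects without a Safety Follow-up (SFU) Visit it ends 28 days after the last dose of study drug. It adds a limit: "Only data collected up to the end of study for a subject will be included in analysis".

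Protocol 10 makes the term broad: "Study drug refers to VX-152, VX-661/IVA, IVA, and their matching placebos". In Cohort 2A the components stop on different days (Protocol Table 3-2): "The last dose of VX-152 or placebo will be the morning dose on Day 15", but "The last dose of VX-661/IVA will be the morning dose on Day 29". Table 3-3 puts the same two stops at Day 29 and Day 43 in Cohort 2B. Between them lies the washout, described in Protocol 8.1.4: "Subjects will continue to receive VX-661/IVA during the Washout Period". SAP Appendix B gives SFU target days of 57 (2A) and 71 (2B).

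SAP 8.5.1 then states: "An adverse event overview table will be provided for the TE period (TE period for the Treatment Period for Part 2) by treatment group". SAP 8.5 says that safety results for the 2A and 2B treatment groups "will be presented separately, and overall".

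**The concern.** The primary objective is the safety of VX-152 in triple combination (TC), and the sample size section names AE incidence as the primary safety endpoint. In Part 2 both arms take VX-661/IVA from run-in through washout. What separates them is VX-152 against its placebo, and that difference ends on Day 15 or Day 29. Events that start weeks later are still counted as treatment-emergent under the VX-152 dose.

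If VX-152 raises AE risk only while it is taken, the added follow-up brings background events to both arms and pulls the two percentages towards each other. No planned summary lets a reader undo this:

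- SAP 8.5.1 has no AE table limited to VX-152 dosing and no exposure-adjusted rate.
- SAP 8.2.4 summarises Part 2 exposure with washout always included, so VX-152 exposure is not isolated.
- The laboratory, ECG and vital-sign threshold tables in SAP 8.5.2 to 8.5.4 use the same TE period.

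Elsewhere the plan does separate phases. Efficacy in SAP 8.3 stops at the last scheduled on-treatment visit. Run-in TEAEs are kept apart from Treatment Period TEAEs. Protocol 8.1.4 treats washout as the time to observe off-treatment effects.

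**Working it through.** **1. The plan's own figures.** Last VX-661/IVA dose plus 28 days: 29 + 28 = 57 (2A) and 43 + 28 = 71 (2B). Both match Appendix B. SAP Table 6-1 also reproduces from 1 − (1 − p)^n: n = 9 gives 37.0, 61.3 and 76.8%; n = 18 gives 60.3, 85.0 and 94.6%. Its footnote ties those incidences to 2 or 4 weeks of treatment, whereas TEAEs are counted over about 8 or 10 weeks.

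**2. Days after the last VX-152/placebo dose.**

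- SFU on target: 57 − 15 = 42 (2A) and 71 − 29 = 42 (2B).
- SFU at ±7 days: 35 to 49 in both cohorts.
- Re-entry to Study 661-110 with no SFU: if end of study is the Day 29 (2A) or Day 43 (2B) visit, 29 − 15 = 14 and 43 − 29 = 14. Protocol 13.1.1.3 describes AE collection up to 28 days after the last dose for subjects without an SFU, so the tail for this group is not certain.

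**3. Share of the window on VX-152.** On target: 15/57 = 26% (2A) and 29/71 = 41% (2B). With a 14-day tail: 15/29 = 52% and 29/43 = 67%.

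**4. Dilution, as an illustration.** The documents give no background rate and no VX-152 effect, so these are assumptions: constant background hazard h = −ln(1 − p)/15, with p the risk per 15 days; hazard doubled on VX-152 days; no carry-over. For a window of D days with d days on VX-152:

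- comparator risk = 1 − exp(−hD)
- TC risk = 1 − exp(−h(D + d))

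Results for p = 10%:

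| Cohort | Window | TC % | Comparator % | Difference (points) | Ratio |
|---|---|---|---|---|---|
| 2A | on VX-152, Days 1–15 | 19.0 | 10.0 | 9.0 | 1.90 |
| 2A | 14-day tail, to Day 29 | 26.6 | 18.4 | 8.2 | 1.44 |
| 2A | to SFU, Day 57 | 39.7 | 33.0 | 6.7 | 1.20 |
| 2B | on VX-152, Days 1–29 | 33.5 | 18.4 | 15.0 | 1.82 |
| 2B | 14-day tail, to Day 43 | 39.7 | 26.1 | 13.6 | 1.52 |
| 2B | to SFU, Day 71 | 50.5 | 39.3 | 11.2 | 1.29 |

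For p from 5% to 15%, the 2A ratio is 1.95 to 1.85 on drug and 1.23 to 1.18 over the full window. For 2B it is 1.91 to 1.73 on drug and 1.34 to 1.23 over the full window. The 2A difference goes from 4.75 to 4.1 points at 5%, and from 12.75 to 8.1 at 15%.

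**5. Reading 200 mg against 300 mg.** The model gives both doses the same daily risk. At p = 10% the TC percentages for 2A and 2B are:

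| Window | 2A % | 2B % | Gap (points) |
|---|---|---|---|
| to SFU (current) | 39.7 | 50.5 | 10.8 |
| on VX-152 only | 19.0 | 33.5 | 14.5 |
| Days 1–15 | 19.0 | 19.0 | 0 |

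Limiting the table to dosing days restores the contrast within a cohort but widens the gap between cohorts. Only a common cut removes that gap.

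**The case against.** The case for leaving the plan alone has real content.

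- **The randomised comparison is sound.** Each cohort is randomised 3:1 against its own VX-661/IVA comparator on the same nominal schedule, and SAP 8.5 presents the cohorts separately. Window length does not favour either arm. This stands: the loss is of contrast, not of validity.
- **The long window has a purpose.** It follows from the definition of study drug, loses no event and catches delayed ones. This also stands, and is why the current table should stay.
- **Safety is descriptive and the groups are small.** No test is affected. Cohort 2A plans 9 TC and 3 comparator subjects, so one comparator subject is 33 percentage points, and a ratio of 1.2 could not be told from 1.9. That limits what any table can show. It also leaves the descriptive percentages and the listings as the evidence, which favours a table that matches exposure.
- **Ratios make the loss look larger than differences do.** This is correct. At 5% background the 2A difference hardly moves (4.75 to 4.1 points).

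Two stronger readings are tempting, and the documents do not support them. First, a reader might infer that the TE definition itself confounds dose with time, because the windows are 57 and 71 days. It does not: the post-VX-152 tail is 42 days in both cohorts, and the 14-day gap is the planned 2-week versus 4-week dosing. Second, a reader might infer that a combined Part 2 TC column will mix 2A subjects in washout with 2B subjects on VX-152 at Day 29. SAP 8.1 defines the 200 mg and 300 mg groups separately, and the by-visit safety displays are by treatment group. What the overall presentation in SAP 8.5 would pool is unclear, so such a column is not clearly planned.

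**Conclusion.** The point holds as a dilution problem with a cheap remedy. In Part 2 the TE window is tied to the last dose of any study drug. On schedule it therefore carries about 42 days off VX-152, and only about 26% (2A) or 41% (2B) of it is time on VX-152. No planned AE table isolates that time. The 42 days is nominal, and follow-up also varies within a cohort because of re-entry to Study 661-110.

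The day counts come straight from the documents. The size of the dilution rests on assumed rates and on an effect confined to dosing days. Carry-over after the last dose would make it smaller.

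The 57 versus 71-day difference matters only when 200 mg is read against 300 mg, or in any pooled-comparator or overall Part 2 column. Part 1, where all study drug stops together on Day 15 and the tail is 43 − 15 = 28 days, is not a simple benchmark: its share on VX-152, 15/43 = 35%, is lower than that of 2B.

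**What to change.** In SAP 8.1 and 8.5.1, keep the current TEAE table and add two for Part 2:

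1. TEAEs by cohort and arm with onset from the first to the last VX-152/placebo dose, with later-onset events of the same TE period shown separately.
2. TEAEs with onset on Days 1 to 15 for 2A and 2B side by side, labelled as the only like-for-like display of 200 mg against 300 mg.

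The second is needed as well as the first, because the first widens the modelled gap between cohorts. Both use AE onset and dosing dates already collected, and nothing in trial conduct changes. The cost is SAP wording, two extra tables and fewer events in the narrower windows.

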	Days -56 to -29 ^e	Day -28 (± 1 day)	Day -14 ^f (± 1 day)	Day 1	Days 3 and 5 ^g (or Days 4/6 or Days 3/6) ^h	Day 8 (± 1 day)	Day 11 ^g (± 1 day)	Day 15 and Day 29 (± 1 day)	Day 43 (± 3 days)		
Urinalysis ^k	X	X		X		X		X	X	X	X
Pregnancy test (all females of childbearing potential)	Serum	Urine		Urine				Urine		Serum	Serum
CFTR genotype ^t	X										
FSH ^u	X										
G6PD activity test ^v	X										
Serum chemistry and hematology ^k	X	X		X	X ^{g,x}	X	X ^{g,x}	X	X	X	X
Coagulation ^k	X	X		X		X		X			X
PK sampling ^y				X		X		X		X ^y	

^s Spirometry may be performed pre- or post-bronchodilator at the Screening Visit. Spirometry will be performed pre-bronchodilator, before the morning dose of study drugs, and should be performed at approximately the same time at every other study visit. On Days 1, 15, and 29, spirometry will be performed pre-bronchodilator 5 hours (± 1 hour) after study drug administration.

^t *CFTR* genotyping will be performed for all subjects. If the screening *CFTR* genotype result is not received before Day -28, a previous *CFTR* genotype laboratory report may be used to establish eligibility.

^u FSH will be measured for any suspected postmenopausal female subjects with at least 12 months of continuous spontaneous amenorrhea.

^v A single blood sample will be collected for the G6PD activity test.

^x On Days 3, 5, and 11, the following parameters will be measured: lactate dehydrogenase, total and direct bilirubin, alkaline phosphatase, aspartate aminotransferase, alanine aminotransferase, and gamma glutamyl transferase.

^y Blood samples will be collected for PK analysis of VX-152, VX-661, M1-661, IVA, and M1-IVA. On Day 1, samples will be collected before dosing (0 hours) and at 1, 2, 4, and 6 hours after dosing (relative to morning dose). On Day 8, a predose sample will be collected before the morning dose of

Table 3-3 Study VX16-152-102: Schedule of Assessments for Part 2, Cohort 2B

Event/Assessment ^a	Screening	Run-in Period		Treatment Period ^b				Washout Period	ETT Visit ^c	Safety Follow-up 28 (± 7) Days After Last Dose ^d
	Days -56 to -29 ^e	Day -28 (± 1 day)	Day -14 ^f (± 1 day)	Day 1	Days 3 and 5 ^g (or Days 4/6 or Days 3/6) ^h	Day 8 (± 1 day)	Day 11 ^g (± 1 day)	Day 15 and Day 29 (± 1 day)		
VX-661/IVA dosing ^z		Day -28 through Day 43								
VX-152 or placebo dosing ^{aa}				Day 1 through Day 29						

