8.2.2 Study Drug Dose and Duration

Part 1 will evaluate up to 3 dose levels of VX-152 (100, 200, and 300 mg q12h) in TC with VX-661/IVA in subjects with the *F508del*/MF genotype. [REDACTED]

The dose escalation of VX-152 is no more than 2-fold. [REDACTED]

Up to 3 dose levels of VX-152 will be evaluated as part of the TC in Part 1 to provide a range of doses and exposures that will enable dose-response and exposure-response analyses for PD (Section 12.1.2.1). Dose- and exposure-response information obtained from Part 1 (*F508del*/MF genotype) is expected to be applicable to other populations with an *F508del* mutation, including *F508del*/*F508del* genotypes, based on similar in vitro potency for the TC in HBE cells with 1 or 2 copies of *F508del*.⁸

The dose of VX-661 and IVA (100 mg qd and 150 mg q12h) in the TC are the same doses currently under evaluation in Phase 3 studies of VX-661/IVA. These doses of VX-661 and IVA are appropriate for evaluation in the TC based on in vitro experiments with VX-152 which evaluated similar levels of VX-661 and IVA exposure after correction for protein-binding.

[REDACTED]
[REDACTED]
[REDACTED] In
Studies VX06-770-101 and VX11-661-101, improvements in sweat chloride and ppFEV₁ were observed as rapidly as 3 to 7 days after the start of dosing, with most of the effect observed within 14 days. Given the increased in vitro response of the TC relative to VX-661/IVA, it is expected that the 2-week treatment duration will be sufficient to observe differences between treatment arms with respect to efficacy and PD endpoints. In addition, based on previous clinical experience, 2 weeks is sufficient for VX-152, VX-661, and IVA to reach steady-state levels of exposure. The 4-week treatment duration in Part 2 Cohort 2B will provide additional safety data for the TC.

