10.4 Study Drug Interruption and Stopping Rules

Subjects with new treatment-emergent ALT or AST elevations of $>3 \times \text{ULN}$, or total bilirubin $>2 \times \text{ULN}$, must be followed closely, including confirmatory testing performed by the central laboratory within 48 to 72 hours of the initial finding and subsequent close monitoring of ALT, AST, and bilirubin levels, as clinically indicated.

If a subject cannot return to the site for confirmatory testing, a local laboratory may be used. Local laboratory results must be reported immediately to the medical monitor, and the subject must have the tests repeated and sent to the central laboratory as soon as possible (ideally within 48 to 72 hours).

Study drug administration **must be interrupted** immediately (prior to confirmatory testing), and the medical monitor must be notified, if any of the following criteria are met:

- ALT or AST $>8 \times$ ULN
- ALT or AST $>5 \times$ ULN for more than 2 weeks
- ALT or AST $>3 \times$ ULN, in association with total bilirubin $>2 \times$ ULN and/or clinical jaundice
- Indirect bilirubin $>2 \times$ ULN (defined as ULN for total bilirubin minus ULN for direct bilirubin)

A thorough investigation of potential causes should be conducted, and the subject should be followed closely for clinical progression.

Study drug administration **must be discontinued**, if confirmatory testing results obtained after study drug interruption meet any of the following criteria:

- ALT or AST $>8 \times$ ULN
- ALT or AST $>5 \times$ ULN for more than 2 weeks
- ALT or AST $>3 \times$ ULN, in association with total bilirubin $>2 \times$ ULN and/or clinical jaundice
- Indirect bilirubin $>2 \times$ ULN (defined as ULN for total bilirubin minus ULN for direct bilirubin), in association with decreased haptoglobin

If an alternative, reversible cause of transaminase elevation and/or increased bilirubin or clinical jaundice has been identified, study drug administration may be resumed once transaminases or bilirubin return to baseline or are $\leq 2 \times$ ULN, whichever is higher. Approval of the medical monitor is required before resumption of study drug.

All subjects in whom treatment is discontinued for elevated transaminases and/or bilirubin should have these levels monitored closely until levels normalize or return to baseline.

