8 STATISTICAL ANALYSIS

8.1 General Considerations

The analysis will be performed for each part, and presented by treatment group, unless specified otherwise. The treatment groups are defined as follows:

- Part 1: *F508del*/MF genotype group
 - VX-152 100mg q12h + VX-661/IVA, VX-152 200mg q12h + VX-661/IVA, VX-152 300mg q12h + VX-661/IVA, and placebo, with VX-661 component administered as 100 mg qd and IVA component administered as 150 mg q12h.
- Part 2: *F508del/F508del* genotype group
 - VX-152 200mg q12h + VX-661/IVA, VX-152 300mg q12h + VX-661/IVA, VX-661/IVA, VX-661/IVA, VX-661/IVA from Cohort 2A and VX-661/IVA from Cohort 2B, with VX-661 component administered as 100 mg qd and IVA component administered as 150 mg q12h.

The Schedule of Assessments is provided in Appendix A. The precision standards for reporting safety and efficacy variables are provided in an internal Biometrics document that specifies the programming rules including the precision for derived variables.

All individual subject data for those randomized or dosed with any amount of study drug will be presented in data listings.

Continuous variables will be summarized using the following descriptive summary statistics: the number of subjects (n), mean, SD, standard error (SE), median, minimum value (min), and maximum value (max). SE may not be reported for safety summary tables.

Categorical variables will be summarized using counts and percentages. Percentages will be presented to 1 decimal place.

Baseline value, unless otherwise specified, will be defined as the most recent non-missing measurement (scheduled or unscheduled) collected before the first dose of study drug on Day 1 of the Treatment Period. For ECG, baseline will be defined as the most recent non-missing measurement (or the average of triplicate measurements, if the most recent non-missing measurement is obtained in triplicate), before the first dose of study drug on Day 1 of the Treatment Period.

Absolute change from baseline will be calculated as postbaseline value – baseline value.

Relative change from baseline will be calculated as (postbaseline value – baseline value)/baseline value.

Treatment-emergent (TE) period for Part 1 will include the time from the first dose of study drug in the Treatment Period to the Safety Follow-up (SFU) Visit, or 28 Days after the last dose of study drug for subjects who do not complete the SFU Visit.

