Appendix H: Criteria for Threshold Analysis

Parameter	Threshold Analysis	Comments
Clinical Chemistry	y (LFT)	
ALT	$>ULN - \leq 3xULN$ $>3x - \leq 5xULN$ $>5x - \leq 8xULN$ $>8x - \leq 20.0xULN$ >20.0xULN	FDA DILI Guidance Jul 2009.
AST	>ULN - $\leq 3x$ ULN > $3x - \leq 5x$ ULN > $5x - \leq 8x$ ULN > $8x - \leq 20.0x$ ULN > $20.0x$ ULN	FDA DILI Guidance Jul 2009.
ALT or AST	$\begin{array}{l} (ALT>ULN - \leq 3xULN) \mbox{ or } (AST>ULN - \leq 3xULN) \\ (ALT>3x - \leq 5xULN) \mbox{ or } (AST>3x - \leq 5xULN) \\ (ALT>5x - \leq 8xULN) \mbox{ or } (AST>5x - \leq 8xULN) \\ (ALT>8x - \leq 20xULN) \mbox{ or } (AST>8x - \leq 20xULN) \\ (ALT>20xULN \mbox{ or } AST>20 \mbox{ xULN} \end{array}$	FDA DILI Guidance
Alkaline Phosphatase	>ULN - \leq 1.5xULN >1.5 - \leq 2.5 xULN >2.5 - \leq 5.0 x ULN >5.0 - \leq 20.0 x ULN >20.0 x ULN	FDA DILI Guidance Jul 2009.
Total Bilirubin	$>ULN - \le 1.5xULN$ $>1.5 - \le 2xULN$ $>2 - \le 3xULN$ $>3 - \le 10xULN$ >10xULN	FDA DILI Guidance Jul 2009.
Direct Bilirubin	$>ULN - \le 1.5xULN$ $>1.5 - \le 2xULN$ $>2 - \le 3xULN$ $>3 - \le 10xULN$ >10xULN	FDA DILI Guidance Jul 2009.
ALT and Total Bilirubin	ALT>3xULN and TBILI>2xULN	FDA DILI Guidance Jul 2009.
AST and Total Bilirubin	AST>3xULN and TBILI>2xULN	FDA DILI Guidance Jul 2009.
(ALT or AST) and Total Bilirubin	(ALT>3xULN or AST>3xULN) and TBILI>2×ULN	FDA DILI Guidance Jul 2009.

Table 11-10 Threshold Analysis Criteria for Laboratory Tests (as applicable)

Parameter	Threshold Analysis	Comments
GGT	>ULN - ≤ 2.5xULN >2.5 - ≤ 5.0xULN >5.0 - ≤ 20.0xULN >20.0xULN	CTCAE grade 1-4
Clinical Chemis	stry (NON-LFT)	
Albumin	$<$ LLN - \ge 30 g/L $<$ 30 - \ge 20 g/L <20 g/L	CTCAE grade 1-3
Amylase	$>1x - \leq 1.5xULN$ $>1.5x - \leq 2xULN$ $>2x - \leq 5xULN$ >5xULN	Criteria based upon CTCAE
Creatinine	>ULN - ≤ 1.5xULN >1.5 - ≤ 3.0xULN >3.0 - ≤ 6.0xULN >6.0xULN	CTCAE grades 1-4
Lipase	>ULN - ≤ 1.5xULN >1.5x - ≤ 2xULN >2x - ≤ 5xULN >5xULN	Criteria based upon CTCAE
Total protein	<lln >ULN</lln 	No CTCAE
Hematology		
Hemoglobin	Hgb decreased (anemia) $<100 - \ge 80 \text{ g/L}< 80 g/L$	CTCAE grade 1-3
	Hgb increased >ULN - ≤ 20 g/L above ULN >20 g/L above ULN - ≤ 40 g/L above ULN >40 g/L above ULN	CTCAE grade 1-3
Platelets	Platelet decreased $<75.0 - \ge 50.0 \times 10e9 /L<50.0 - \ge 25.0 \times 10e9 /L<25.0 \times 10e9 /L$	CTCAE grade 1-4
	Platelet increased >ULN	No CTCAE available
Reticulocytes	<lln >ULN</lln 	No CTCAE

 Table 11-10
 Threshold Analysis Criteria for Laboratory Tests (as applicable)

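### The SAP's safety rule for 5-hour post-dose ppFEV1 stops at Day 15, although Cohort 2B also collects it on Day 29

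*SAP*

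**What the plan says.** SAP 8.1 gives ppFEV1 two roles. For efficacy, the visit windows of Appendix B apply. For safety, the rule is: "For safety analysis, the assessments at 5 hours post-dose on nominal days 1 and 15 will be used". No exception is made for any cohort.

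The schedule for Cohort 2B is longer. Protocol Table 3-3, footnote s, reads: "On Days 1, 15, and 29, spirometry will be performed pre-bronchodilator 5 hours (± 1 hour) after study drug administration". SAP Table 11-3 repeats that footnote. Part 1 (Protocol Table 3-1) and Cohort 2A (Protocol Table 3-2) have the 5-hour reading on Days 1 and 15 only.

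In SAP Appendix B, the Cohort 2B spirometry rows show a pre-dose and a 5-hour time point at Day 15, but Day 29 carries no post-dose time point.

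Protocol 8.2.2 gives the reason for the longer cohort: "The 4-week treatment duration in Part 2 Cohort 2B will provide additional safety data for the TC".

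Two other provisions bear on where the Day 29 values could appear. SAP 8.3 keeps same-day post-dose values out of the model-based analyses. SAP 8.1 also provides that "All individual subject data for those randomized or dosed with any amount of study drug will be presented in data listings".

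**The concern.** The safety rule fits the two-week cohorts and misses the one occasion that only the four-week cohort has. Day 29 is the only post-dose spirometry after four weeks of VX-152. A post-dose reading shows what happens to lung function in the hours after a dose, which the pre-dose reading on the same day cannot show.

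A programmer who follows SAP 8.1 literally would leave the Day 29 readings out of the safety output. Adding them later would be a choice made after the data had been seen. Safety is the primary objective, and Cohort 2B was lengthened to add safety data, so the plan should say in advance how these readings are used.

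**Working it through.** The plan states no figure on this point, so the check sets the schedule against the rule and counts what is left out.

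**Step 1. Schedule against rule**

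| Group | Days with a 5-hour reading | Days used for safety (SAP 8.1) | Left out |
|---|---|---|---|
| Part 1 | 1, 15 (Protocol Table 3-1, footnote q) | 1, 15 | none |
| Cohort 2A | 1, 15 (Protocol Table 3-2, footnote s) | 1, 15 | none |
| Cohort 2B | 1, 15, 29 (Protocol Table 3-3 and SAP Table 11-3, footnote s) | 1, 15 | 29 |

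**Step 2. Is Day 29 on treatment?** Yes, in Cohort 2B. Protocol Table 3-3, footnote aa, places the final VX-152 or placebo dose on the morning of Day 29, so the 5-hour reading follows a study dose. In Cohort 2A, Day 29 is the end of the Washout Period and no 5-hour reading is scheduled. Any added wording must therefore be limited to Cohort 2B.

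**Step 3. Appendix B.** Of all the spirometry rows there, only Day 15 in Cohort 2B carries a 5-hour label. These rows sit under the efficacy heading, and SAP 8.1 uses nominal days for safety, so Appendix B does not itself decide the safety use. It does need to agree with SAP 8.1 once that section is changed.

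**Step 4. Size.** Planned Cohort 2B numbers (Protocol Figure 8-1) are 24 subjects, 18 on triple combination and 6 on comparator.

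- Scheduled 5-hour readings: 24 × 3 = 72
- Used under SAP 8.1: 24 × 2 = 48
- Left out: 72 − 48 = 24, and 24/72 = one third
- By arm: 18 of 18 × 3 = 54 on triple combination, and 6 of 6 × 3 = 18 on comparator

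**The case against.** The strongest reply is that no protocol commitment is broken. Spirometry is not among the safety evaluations in Protocol 11.7 or the safety endpoints in Protocol 12.3.5, SAP 5.2 and SAP 8.5. SAP 8.1 therefore already offers more than the protocol asks for, and Days 1 and 15 are the two days that every cohort shares. This stands, and it is the main reason the point is minor. It does not explain leaving Day 29 out. SAP 8.5 presents Cohorts 2A and 2B separately as well as overall, so an extra day for Cohort 2B would not disturb the common days, and the SAP gives no reason for the restriction.

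It can also be said that little is lost. Protocol 8.2.2 expects steady-state exposure within two weeks, so Day 15 already shows the post-dose response at that level. SAP 8.3.1.1 analyses pre-dose ppFEV1 on Day 29 as part of the average through Day 29. Both points stand and limit the weight.

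A reader might infer that the Day 29 post-dose values would appear nowhere but in listings. The documents do not support so firm a statement. SAP 8.1 has a general provision for descriptive summaries of continuous variables, the bar in SAP 8.3 covers only model-based analyses, and parts of the SAP are missing from the public copy. What can be said is that the explicit safety rule excludes Day 29 and no visible text puts it back.

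**Conclusion.** The point holds as a minor gap in the SAP's safety rule. As written, one third of the planned Cohort 2B post-dose spirometry falls outside the safety analysis. That count assumes full enrolment to the planned numbers, no missed visits and no early discontinuation; actual numbers may be lower. No estimate, test, power figure or type I error rate is affected, because the safety analysis is descriptive.

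A reader comparing Protocol 10.4 with SAP Appendix H might also infer a second error. Protocol 10.4 requires dosing to be interrupted "immediately (prior to confirmatory testing), and the medical monitor must be notified, if any of the following criteria are met". One criterion is indirect bilirubin above twice its upper limit of normal (ULN), with that limit "defined as ULN for total bilirubin minus ULN for direct bilirubin". Table 11-10 has rows for total and direct bilirubin but none for indirect. The documents do not make this an error:

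- Nothing requires Appendix H to mirror Protocol 10.4, and Protocol 12.3.5.2 leaves the criteria and the choice of parameters to the SAP.
- The liver rows cite drug-induced liver injury guidance or CTCAE. The row "ALT>3xULN and TBILI>2xULN" overlaps with Protocol 10.4 but is attributed to that guidance.
- Total and direct bilirubin are both measured (Protocol Table 11-2), so indirect bilirubin can be derived from the listed values.

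The existing rows would not give a by-arm count of subjects meeting that criterion, since none combines total with direct bilirubin. How many subjects that concerns cannot be worked out, because the documents give no ULN values. An extra row is an optional reporting aid.

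**What to change.** 1. In SAP 8.1, name nominal Days 1 and 15 for all cohorts and, for Cohort 2B only, Day 29 as well.
2. In SAP Appendix B, add the 5-hour post-dose time point to the Day 29 spirometry row for Cohort 2B, so that the two places agree.
3. State that the 5-hour post-dose ppFEV1 values will be summarised descriptively by treatment group.

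If Day 29 was left out on purpose, one sentence giving the reason would serve instead.

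The cost is one phrase, one row label and one small descriptive table, made by SAP amendment before database lock as SAP section 3 allows. All the data are already scheduled for collection. Visits, sample size, hypothesis tests and clinical rules stay as they are.

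As a suggestion only, the sponsor could add to Table 11-10 a derived indirect-bilirubin row (total minus direct, with the ULN as Protocol 10.4 defines it) at that section's existing cut-point.
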